11. SUBJECT: ADDITION OF NON-SERIOUS ADVERSE EVENTS OF SPECIAL INTEREST

REASON FOR CHANGE:

In response to safety requests and the current protocol template, several safety sections have been updated to include the assessment and reporting of non-serious events of special interest (AESI).

SECTION 5.1. SAFETY PARAMETERS AND DEFINITIONS,

New text:

Safety assessments will consist of monitoring and recording adverse events, including serious adverse events (systemic and ocular);, *non-serious adverse events of special interest*; measurement of protocol-specified safety laboratory assessments; measurement of protocol-specified vital signs (SBP, DBP), ECGs, and other protocol-specified tests that are deemed critical to the safety evaluation of the study (i.e., regular ophthalmological monitoring [ocular safety panel and SD-OCT assessments]).

Certain types of events require immediate reporting to the Sponsor, as outlined in Section 5.4.

Old text:

Safety assessments will consist of monitoring and recording adverse events, including serious adverse events (systemic and ocular); measurement of protocol-specified safety laboratory assessments; measurement of protocol-specified vital signs (SBP, DBP), ECGs, and other protocol-specified tests that are deemed critical to the safety evaluation of the study (i.e., regular ophthalmological monitoring [ocular safety panel and SD-OCT assessments]).

Certain types of events require immediate reporting to the Sponsor, as outlined in Section 5.4.

SECTION 5.1.3 NON-SERIOUS ADVERSE EVENTS OF SPECIAL INTEREST (IMMEDIATELY REPORTABLE TO THE SPONSOR),

New text:

*Non-serious adverse events of special interest are required to be reported by the investigator to the Sponsor immediately (i.e., no more than 24 hours after learning of the event; see Section **Error! Reference source not found.** for reporting instructions). Adverse events of special interest for this study include the following:*

- *Cases of an elevated ALT or AST in combination with either an elevated bilirubin or clinical jaundice, as defined in Section **Error! Reference source not found.** (Abnormal Liver Function Tests)*
- *Suspected transmission of an infectious agent by the study drug, as defined below: Any organism, virus, or infectious particle (e.g., prion protein transmitting transmissible spongiform encephalopathy), pathogenic or non-pathogenic, is considered an infectious agent. A transmission of an infectious agent may be suspected from clinical symptoms or laboratory findings that indicate an infection in a patient exposed to a medicinal product. This term applies only when a contamination of the study drug is suspected.*
- *The Safety Science Responsible for the program is accountable for determining the non-serious Adverse Events of Special Interest (AESI) for a protocol.*

Old text:

None

SECTION 5.4. IMMEDIATE REPORTING REQUIREMENTS FROM INVESTIGATOR TO SPONSOR,

New text:

Certain events require immediate reporting to allow the Sponsor to take appropriate measures to address potential new risks in a clinical trial. The investigator must report such events to the Sponsor immediately; under no circumstances should reporting take

place more than 24 hours after the investigator learns of the event. The following is a list of events that the investigator must report to the Sponsor within 24 hours after learning of the event, regardless of relationship to study drug:

- Serious adverse events
- *non-serious adverse events of special interest*
- Sight-threatening adverse events
- Pregnancies

Old text:

Certain events require immediate reporting to allow the Sponsor to take appropriate measures to address potential new risks in a clinical trial. The investigator must report such events to the Sponsor immediately; under no circumstances should reporting take place more than 24 hours after the investigator learns of the event. The following is a list of events that the investigator must report to the Sponsor within 24 hours after learning of the event, regardless of relationship to study drug:

- Serious adverse events
- Sight-threatening adverse events
- Pregnancies

SECTION 5.4.2 REPORTING REQUIREMENTS FOR SERIOUS ADVERSE EVENTS, NON-SERIOUS ADVERSE EVENTS OF SPECIAL INTEREST, AND SIGHT-THREATENING ADVERSE EVENTS,

New text:

For reports of serious adverse events, *non-serious adverse events of special interest*, and sight-threatening adverse events (see Sections 5.1.2 and 5.1.3), investigators should record all case details that can be gathered on the Serious Adverse Reporting Form and forward this form to the Serious Adverse Event Responsible within 24 hours.

Old text:

For reports of serious adverse events and sight-threatening adverse events (see Sections 5.1.2 and 5.1.3), investigators should record all case details that can be gathered on the Serious Adverse Reporting Form and forward this form to the Serious Adverse Event Responsible within 24 hours.

SECTION 5.5.2. SPONSOR FOLLOW-UP,

New text:

For serious adverse events, *non-serious adverse events of special interest*, sight-threatening adverse events, and pregnancies, the Sponsor or a designee may follow up by telephone, fax, electronic mail, and/or a monitoring visit to obtain additional case details and outcome information (e.g., from hospital discharge summaries, consultant

reports, autopsy reports) in order to perform an independent medical assessment of the reported case..

Old text:

For serious adverse events, sight-threatening adverse events, and pregnancies, the Sponsor or a designee may follow up by telephone, fax, electronic mail, and/or a monitoring visit to obtain additional case details and outcome information (e.g., from hospital discharge summaries, consultant reports, autopsy reports) in order to perform an independent medical assessment of the reported case.

SECTION 5.6. POST-STUDY ADVERSE EVENTS,

New text:

The investigator is not required to actively monitor patients for adverse events after the end of the adverse event reporting period (*as defined as 28 days after the last dose of study drug*)~~in Section 5.3.1~~. However, the Sponsor should be notified if the investigator becomes aware of any death or any other serious adverse event, *or sight-threatening adverse events reportable to the Sponsor* occurring after the end of the adverse event reporting period, if the event is believed to be related to prior study drug treatment. *The event should be reported directly to the Sponsor or its designee, either by faxing or by scanning and emailing the Serious Adverse Event Reporting Form using the fax number or email address provided to investigators.*

Old text:

The investigator is not required to actively monitor patients for adverse events after the end of the adverse event reporting period (defined as 28 days after the last dose of study drug). However, the Sponsor should be notified if the investigator becomes aware of any death or any other serious adverse event occurring after the end of the adverse event reporting period, if the event is believed to be related to prior study drug treatment.

12. SUBJECT: EDITORIAL CHANGES

REASON FOR CHANGE:

- alignment with protocol template
- correction of typos
- references added
- changes for general updates and clarifications
- changing of study treatment to study drug throughout the document as sham injection was removed

- Appendix 2 removed

applicable to section: glossary,

1. Background and Rationale, 1.1 Background on Disease, 1.2 Background on RO6867461, 1.2.2. Previous Clinical Studies, 1.2.2.1 Safety and Tolerability, 3.2. Rationale for Study Design, 3.2.1. Rationale for Dosage selection, 3.3.1. Safety Outcome Measures, 4.2.2. Exclusion Criteria, 4.3.2. Treatment Administration Procedure, 4.4.1.1. RO6867461 and Placebo, 4.4.1.2 Ranibizumab Active Comparator, 4.4.2.1. RO6867461 and Ranibizumab, 4.5.1 Permitted Therapy, 4.6 Study Assessments, 4.6.1.1 Medical History and demographic Data, 4.6.1.3. Vital Signs, [REDACTED]
[REDACTED] 4.6.5 Disease-Specific Assessments, 4.6.5.2.1. Best Corrected Visual Acuity, 4.6.7.1. Screening and Pretreatment Assessments, 4.6.7.3 Assessments at Early Termination Visit, 4.7.1 Patient Discontinuation, 4.7.1.1. Discontinuation from study Drug, 5.1.1. Adverse Events, 5.3.5.4. Abnormal Laboratory Values, 5.3.5.5. Abnormal Vital Sign Values, 5.6 Post-Study adverse Events, 5.7. Expedited Reporting to Health authorities, Investigators, Institutional Review Boards, and Ethics Committees, 6.3.1. Safety Analysis Population, 6.3.2 Efficacy, Pharmacokinetic, and Pharmacodynamics Analysis Population, 10. References, Appendix 2 Schedule of Assessment Detail Table

3.7	Missing Data.....	14
3.8	Interim Analyses	14
	APPENDIX	15

LIST OF TABLES

Figure 1	Study Design.....	4
----------	-------------------	---

Background

This Statistical Analysis Plan (SAP) documents the statistical methods for summarizing and analyzing the efficacy and safety data from study BP30099. The main purpose of this SAP is to describe the data handling rules, derivation rules, and statistical analysis methods.

1. **STUDY DESIGN**

This is a multiple-center, multiple-dose, randomized, active comparator-controlled, double-masked, three parallel group, 36-week study in patients with CI-DME.

[figure not shown]
The three groups of this study are as follows (see [Figure 1](#)):

- Arm A: 0.3 mg ranibizumab IVT
- Arm B: 1.5 mg RO6867461 IVT
- Arm C: 6 mg RO6867461 IVT

This study will consist of a treatment period (20 weeks) and an observational period (up to 16 weeks), for a total study length of up to 36 weeks. During the treatment period, the study drug will be administered to the patients on Day 1 and on every 4th week, for a total of 6 injections. During the observational period, patients will be evaluated every 4th week. If during any of these evaluations the patients meet the pre-specified criteria, the patients will receive a single dose of 0.3 mg ranibizumab, and exit the study. They will receive a follow up phone call 7 days after the dose of ranibizumab to evaluate any potential adverse events. Otherwise, patients will exit the study once they have completed the observational visit at week 36.

Only one eye will be selected as the study eye.

Figure 1 Study Design

Q4W=every 4 weeks.

The total duration of the study for each patient will be up to 40 weeks, divided as follows (see Figure 1):

- Screening: Up to 4 weeks
- Baseline: Day 1
- Study treatment administration period: From Day 1 to Week 20
- Observational period: From Week 20 up to Week 36
- Safety follow up call: During the observational period and 7 days after ranibizumab administration

Patients will be admitted to the investigational site on Day 1 and for subsequent scheduled visits and will be discharged the same day after all mandatory and safety assessments, as specified in the Schedule of Assessments (SoA; see 0), are completed.

If a site has an unexpected issue (e.g., the interactive voice and web response system (IxRS) is not able to assign the study kit), the patient's study treatment may be administered within 3 working days of the scheduled treatment visit with the Medical Monitor's permission. The interval between two study treatment administrations needs to be at least 21 days.

1.1 PROTOCOL SYNOPSIS

The Protocol Synopsis is described in Appendix 1. For additional details, see the Schedule of Assessments in Appendix 2.

1.2 OUTCOME MEASURES

1.2.1 Safety Outcome Measures

The safety outcome measures for this study are as follows:

- Any relevant safety observations derived from BCVA (modified ETDRS charts), slit-lamp examination, dilated binocular indirect high-magnification ophthalmoscopy, intraocular pressure (IOP), fundus photography (FP), SD-OCT, and angiography
- Incidence and severity of ocular adverse events
- Incidence and severity of non-ocular adverse events
- Incidence of laboratory abnormalities, based on hematology, clinical chemistry, and urinalysis test results
- Incidence of anti-RO6867461 antibodies
- ECGs
- Vital signs

1.2.2 Pharmacokinetic Outcome Measures

The pharmacokinetic (PK) outcome measures for this study are as follows:

- PK profiles and parameters derived from the nonlinear mixed effects modeling approach following IVT administration of RO6867461, including the following parameters:

Primary parameters: Clearance (CL) and volume (V)

Secondary parameters: Maximum concentration observed (C_{max}), area under the concentration-time curve from time 0 to infinity (AUC_{0-inf}), AUC_{0-t} , time to maximum concentration (t_{max}), $t_{1/2}$

Compartmental analysis to assess IVT concentrations, as appropriate (exploratory)

[REDACTED]

1.2.3 Efficacy and Pharmacodynamic Outcome Measures

The primary analysis population will be treatment naïve patients. Additional analyses may be performed in the overall population and in patients previously treated with IVT anti-VEGF.

1.2.3.1 Primary Efficacy Outcome Measure

The primary efficacy outcome measure is the mean change in BCVA (ETDRS letters) from baseline at Week 24 in treatment-naïve patients.

RO6867461—F. Hoffmann-La Roche Ltd

Statistical Analysis Plan BP30099

1.2.3.2 Secondary Efficacy Outcome Measures

The secondary efficacy outcome measures include functional (BCVA) and anatomical (PD imaging) measures relevant to the mechanism of action of RO6867461 as follows:

BCVA:

- Proportion of patients gaining ≥ 15 letters from baseline BCVA at Week 24
- Proportion of patients with BCVA ≥ 69 letters (20/40 or better) at Week 24
- Proportion of patients with BCVA ≥ 84 letters (20/20 or better) at Week 24

Anatomic outcome measures by SD-OCT:

- Mean change from baseline in foveal center point thickness at Week 24
- Mean change from baseline in mean CST (1 mm diameter) at Week 24
- Proportion of patients with resolution of subretinal and intraretinal fluid at Week 24

Anatomic outcome measures by FFA:

- Proportion of patients with resolution of leakage at the macula at Week 24
- Change from baseline in the size of the foveal avascular zone at Week 24

Table 1 Description of Secondary Outcome Measures

Secondary EndPoint	Detailed Definition	Variable names used by central reading center
Foveal Center Point thickness (Central Foveal Thickness)	Thickness from Inner Limiting Membrane to the Retinal Pigment Epithelial at the horizontal slice closest to the center of the fovea	OCTCentralRetinalThickness1-3
mean CST	Mean thickness from Inner Limiting Membrane to the Retinal Pigment Epithelial over the 1 mm central subfield	OCTCentralSubfieldThickness1-3
intra-retinal fluid (IRF)	Presence of fluid within the retina	OCTIntraRetinalFluid
sub-retinal fluid SRF)	Presence of fluid between the retina and the retinal pigment epithelium	OCTSubretinalFluidThicknessNotPresent
Resolution of leakage at the macula	Resolution of fluorescein leakage at the macula	FAMaculaMLEakageArea1-3 or FAMaculaMLEakage
Size of the foveal avascular zone	Size of the foveal avascular zone (FAZ) by FFA	FAMaculaFAZArea1-3 FAMaculaFAZAreaB1-3

1.2.3.3 Pharmacodynamic Biomarker Outcome Measure

Plasma PD biomarker outcome measure for this study is as follows:

- Change in plasma levels of VEGF and Ang-2

1.2.4 Exploratory Outcome Measures

The exploratory outcome measures for this study include but are not limited to the following:

BCVA:

- Difference in mean BCVA change from baseline between the treatment-naïve patients and patients with previous IVT anti-VEGF (differential effect of RO6867461)
- Proportion of patients with BCVA ≥ 69 letters (20/ 40 or better) over time
- Proportion of patients with BCVA ≥ 84 letters (20/ 20 or better) over time

Disease-related exploratory outcome measure:

- Proportion of patients with DR severity improvement from baseline on the ETDRS-DRSS (diabetic retinopathy severity score) at Week 24

Anatomic exploratory outcome measures:

- Change from baseline in macular perfusion and leakage by FFA at Week 12
- Change from baseline in peripheral perfusion and leakage by FFA at Week 24

Durability-related exploratory outcome measures:

- Time to increase in CST by $\geq 50\mu\text{m}$ and/ or loss of ≥ 5 letters of BCVA due to DME compared to values at Week 20
- Time to treatment with 0.3 mg ranibizumab after Week 20

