2.3 EXPLORATORY OBJECTIVES

The exploratory objectives for this study are as follows:

- *To explore the predictive effect of previous IVT anti-VEGF treatment on efficacy of RO6867461*
- *To evaluate the efficacy and safety of RO6867461 compared with the active comparator in patients with CI-DME with previous IVT anti-VEGF treatment.*
- 

- [REDACTED]
- [REDACTED]
- [REDACTED]
- To evaluate improvement in DR severity score

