4.3 METHOD OF TREATMENT ASSIGNMENT AND MASKING

4.3.1 Treatment Assignment

After written informed consent has been obtained, all patients will receive a screening number assigned through the interactive voice and web response system (IxRS).

A patient must satisfy all eligibility criteria (see Section 4.2.1 and Section 4.2.2) at the screening or Day 1 visit (as defined for each individual criterion in Section 4.2 and below) prior to randomization and first study treatment (see Section 4.6.7.1). As part of the screening process, FP, FFA, and SD-OCT will be transferred to the central reading center, and a set of images will be evaluated to provide an objective, masked assessment of certain eligibility criteria.

Only one eye will be selected as the study eye. See Section 4.6.7.1 for details.

After all patient eligibility requirements are confirmed on Day 1 visit (see Section 4.2), including:

- Baseline BCVA letter score of 73 to 24 letters (inclusive) in the study eye
- Absence of active intraocular inflammation in the study eye
- Absence of febrile illness within one week prior to Day 1,

the site personnel will contact the IxRS for assignment of a patient identification number (a separate number from the screening number).

Treatment naïve patients will be randomized in a 1:1:1 ratio to one of the arms A, B and C, respectively. Patients previously treated with IVT anti-VEGF will be randomized in a 1:1 ratio to arms A and C.:

- Arm A: 0.3 mg ranibizumab IVT
- Arm B: 1.5 mg RO6867461 IVT

RO6867461—F. Hoffmann-La Roche Ltd
37/Protocol BP30099, Version 3

- Arm C: 6 mg RO6867461 IVT

This study will consist of a treatment period (20 weeks) and an observational period (up to 16 weeks), for a total study length of up to 36 weeks. During the treatment period, the study drug will be administered to the patients on Day 1 and on every 4th week, for a total of 6 injections. During the observational period, patients will be evaluated every 4th week. If during any of these evaluations the patients meet the pre-specified criteria (see Section 4.3.1.1), the patients will receive a single dose of 0.3 mg ranibizumab and exit the study. They will receive a follow up phone call 7 days after the dose of ranibizumab to evaluate any potential adverse events. Otherwise, patients will exit the study once they have completed the observational visit at week 36.

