3.4 GENERAL CONSIDERATIONS

3.4.1 Visit Windows

Visit windowing will be performed for this study with nominal visits/assessments falling outside of allowable protocol-defined visit windows, being reassigned to an appropriate visit for use in analyses.

If multiple valid (non-missing) values for a variable are recorded in the same visit window, one record will be selected for summary/analysis of the data by the following priority:

- The originally scheduled visit assessment

- The assessment closest to the target/planned assessment day.

If scheduled assessments were grouped into multiple visits, the assessments will be assigned to a single visit provided all assessments fall within the same visit window.

Note that unscheduled visits could potentially be included in summaries and analyses following the application of these visit assignment rules.

Assessments that fall outside of the protocol-defined visit windows will be assigned to the closest target visit.

Unless otherwise specified, all analyses and summaries involving visit, will use visits assigned after visit windowing has been performed.

3.4.2 **Baseline**

The baseline measurement is the latest non-missing observation before the first dose of study medication.

3.5 **EFFICACY ANALYSIS**

The List of Planned Outputs (LoPO) contains the full list of reports for the efficacy analysis.

The primary and secondary efficacy analyses will include all randomized treatment-naïve patients, with patients grouped according to the treatment assigned at randomization. Patients with previous IVT anti-VEGF will be analyzed separately. Unless there is strong evidence for RO6867461 effect modification by previous IVT anti-VEGF, primary efficacy analyses will be repeated in all randomized patients (see 3.5.3).

3.5.1 **Primary Efficacy Endpoint**

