3.5.3 Exploratory Efficacy Endpoints

Time to event endpoints will be tested with a two-sided stratified log rank test using the randomization stratification factors BCVA ETDRS letter score (64 letters or better vs. 63 letters or worse) and previous macular laser treatment as strata. Kaplan Meier curves will be displayed, and median time to event estimates will be computed.

Effect modification will be tested in the overall (treatment-naïve and previously treated combined) ITT population by adding a previous IVT anti-VEGF treatment status and a treatment arm by visit by previous IVT anti-VEGF treatment status interaction terms to the Linear model described in section 3.5.1. The treatment arm by visit by previous IVT anti-VEGF treatment status interaction term will be tested at a 10% significance level.

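### The exploratory outcome labelled as the differential effect of RO6867461 is written as a plain difference between populations, and the planned interaction test only partly makes up for it

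*SAP*

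**What the plan says.** **Definition.** SAP 1.2.4 gives the outcome as "Difference in mean BCVA change from baseline between the treatment-naïve patients and patients with previous IVT anti-VEGF (differential effect of RO6867461". Protocol 3.3.4, the protocol synopsis and its copy in SAP Appendix 1 have the same bullet. None names an arm, a comparator or a visit.

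**Objective.** Protocol 2.3: "To explore the predictive effect of previous IVT anti-VEGF treatment on efficacy of RO6867461".

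**Allocation.** Treatment-naïve patients go 1:1:1 to Arms A, B and C, about 50 each. In Protocol 4.3.1, "Patients previously treated with IVT anti-VEGF will be randomized in a 1:1 ratio to arms A and C", about 30 each.

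**Analysis.** SAP 3.5.3: "Effect modification will be tested in the overall (treatment-naïve and previously treated combined) ITT population", by adding prior status and "treatment arm by visit by previous IVT anti-VEGF treatment status interaction terms to the Linear model described in section 3.5.1". The "interaction term will be tested at a 10% significance level". Protocol 6.7.2 plans the same three-way term. Neither section asks for a Week 24 estimate of the difference in drug effect, or for an interval.

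**Use.** SAP 3.5, pointing to 3.5.3: "Unless there is strong evidence for RO6867461 effect modification by previous IVT anti-VEGF, primary efficacy analyses will be repeated in all randomized patients".

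**The concern.** A predictive effect is a difference between populations in the drug-versus-control difference. The bullet describes a difference between populations in outcome. Prior treatment was not randomised, so that quantity mixes prognosis with drug effect.

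An example with invented figures: naïve patients gain 10 letters on Arm A and 14 on Arm C; previously treated patients gain 5 and 9. Within Arm C the bullet gives 14 − 9 = 5 letters. The drug effect is 14 − 10 = 4 in one population and 9 − 5 = 4 in the other, a differential of 0.

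The amendment history says the previously treated patients were added so that their results could guide later development and Phase 3 design. If eyes treated before simply gain less on either drug, a number labelled as a differential drug effect could be taken to show that RO6867461 loses benefit in them.

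**Working it through.** **1. The plan's own figure.** Inputs from SAP 1.3: 50 per arm, 10% drop-out, SD 11, difference 5, one-sided 10%.
- Completers: 50 × 0.9 = 45 per arm.
- SE = 11 × √(2/45) = 2.32. Power = Φ(5/2.32 − 1.28) = 0.81, against the stated 80%.
- Minimum detectable difference = 1.28 × 2.32 = 2.97, against the stated 3 letters or so.

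Both reproduce. The documents give no figure for the naïve versus previously treated comparison. Applying the same drop-out there gives 30 × 0.9 = 27 per arm.

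**2. What the written outcome equals.** Let D be the naïve minus previously treated difference on ranibizumab, eB and eC the drug effects over Arm A in naïve patients, and I the true difference in the Arm C effect (naïve minus previously treated). Write m for the naïve mean on Arm A.
- Within Arm C: (m + eC) − (m − D + eC − I) = D + I.
- Pooled over arms: [m + (eB + eC)/3] − [m − D + (eC − I)/2] = D + (eB + eC)/3 − (eC − I)/2.
- Difference in differences: eC − (eC − I) = I.

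The documents give no value for D; 0 to 6 letters is assumed. With I = 0 and eB = eC = 5:

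| D | Within Arm C | Pooled | Difference in differences |
|---|---|---|---|
| 0 | 0 | 0.83 | 0 |
| 2 | 2 | 2.83 | 0 |
| 4 | 4 | 4.83 | 0 |
| 6 | 6 | 6.83 | 0 |

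The 0.83 at D = 0 is 10/3 − 5/2, the result of comparing three naïve arms with two previously treated arms.

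**3. Precision** (SD 11; 45 and 27 completers per arm).
- Within Arm C: SE = 11 × √(1/45 + 1/27) = 2.68.
- Pooled: SE = 11 × √(1/135 + 1/54) = 1.77.
- Difference in differences: SE = 11 × √(2/45 + 2/27) = 3.79; 80% half-width = 1.2816 × 3.79 = 4.85 letters.
- At two-sided 10%, the last has about 37% power for I = 5 and needs about 9.4 letters for 80% power.

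The plain differences look more precise, but they estimate something else.

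**4. The SAP 3.5.3 test as listed.** Assume seven post-baseline visits to Week 24 (Day 7 and Weeks 4, 8, 12, 16, 20, 24). Five arm-by-status cells × 7 visits give 35 means.
- Without the three-way term: 1 + 6 (visit) + 2 (arm) + 12 (arm by visit) + 1 (status) = 22 parameters. The three-way term therefore carries 35 − 22 = 13 df.
- With status by visit added (6): 35 − 28 = 7 df.
- With status by arm also added (1): 35 − 29 = 6 df, the pure three-way part.

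Six of the 13 df are thus status by visit, which is prognosis and not effect modification. With I = 0, a population gap rising to D by Week 12, and compound symmetry with correlation 0.5 to 0.8 (all assumed), rejection at nominal 10% is:
- D = 2: 19% to 35%
- D = 4: 51% to 91%
- D = 6: 87% to 99.9%

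Adding status by visit brings it back to 10%.

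**The case against.** Outcome lists in these documents are shorthand. The primary outcome bullet does not mention ranibizumab either; its comparison with Arm A is set in the analysis section. On that convention the bracketed label points to the interaction analysis, which includes Arm A. No analysis section plans to subtract one population's mean from the other's. SAP 3.5 also analyses previously treated patients separately. If that uses the primary model, both Arm C minus Arm A estimates will be reported, and a reader could subtract them. The List of Planned Outputs, which is not in these documents, might include the contrast.

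Most of this stands and limits the consequence. It does not rescue the bullet. The primary bullet names no contrast, so the analysis section can supply one; this bullet names a contrast, and it differs from the one analysed. Nor does the interaction test supply an effect size.

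A reader might go further and infer that the trial will report a prognostic gap as a drug effect. For a gap of 5 letters, an 80% interval within Arm C would exclude zero in the wrong direction with probability Φ(5/2.68 − 1.28) = 0.72. The documents do not support that inference: the gap is assumed, and no section specifies that interval. It would also be too strong to say that the bullet measures only how the populations differ whatever the drug, since within Arm C it is D + I and includes the true interaction.

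**Conclusion.** The outcome as defined does not measure effect modification, does not answer the objective in Protocol 2.3, and does not match the analysis in SAP 3.5.3 and Protocol 6.7.2. Its error is D letters within Arm C. Pooled, it is D + 0.83 letters under equal 5-letter drug effects and no interaction.

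The interaction test covers the gap only in part. No Week 24 estimate or interval is specified, and as listed the test can reject because the populations' courses differ over visits. Under SAP 3.5 such a rejection could also decide whether the primary analysis is repeated in all randomised patients. The size of that inflation rests on the assumed gap, its time course and the correlation, and on the model being fitted with exactly the listed terms; a programmer who adds the lower-order terms as a matter of course would remove it.

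This is worth correcting because of how the results are meant to be used. It concerns one exploratory outcome, and the primary comparison in naïve patients and its sample size are untouched.

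**What to change.** 1. In SAP 1.2.4, Protocol 3.3.4 and both synopses, redefine the outcome as the difference between treatment-naïve and previously treated patients in the Arm C minus Arm A difference in BCVA change from baseline at Week 24. Estimate it from Arms A and C with an 80% interval, the level used in SAP 3.5.1.
2. In SAP 3.5.3 and Protocol 6.7.2, add prior-status-by-visit and prior-status-by-arm terms. With both in the model, the three-way term alone tests only whether effect modification changes across visits. Apply the 10% test to the Week 24 contrast, or to the status-by-arm and three-way terms jointly, and say which.
3. Show any within-arm difference between populations as descriptive, without the differential-effect label.

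The cost is wording, two model terms and one contrast, with no new data. The downside is a wider interval: SE 3.79 against 2.68 within Arm C or 1.77 pooled, so about ±4.9 letters at 80%. That width shows how little about 60 previously treated patients can say about effect modification.
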